# 5.2. Laboratory Data

Laboratory data will be collected following the event schedule in Appendix 9.1. Data summaries and listings will be provided in International System of Units (SI). All laboratory data will be listed.

Laboratory assessment values of the form of "<  $x, \le x$ " (i.e., below the lower limit of quantification) or ">  $x, \ge x$ " (i.e., above the upper limit of quantification) will be imputed as "x" in the calculation of summary statistics. For listings, however, the original ranges (i.e., "<  $x, \le x$ " or ">  $x, \ge x$ ") as stated in the database will be presented.

#### 5.2.1. Absolute Value and Change from Baseline

Absolute values and change from baseline (CFB) in hematology, chemistry, and urinalysis continuous variables will be summarized descriptively at each scheduled visit by the optimized dose group and overall. Insulin and Prolactin will be summarized at each scheduled visit by sex and by the optimized dose group and overall.

For visit-based summary tables, in the event of repeat assessments within visit window, the first non-missing value will be used in the tabulations. Results from unscheduled visits will not be included in this summary.

All laboratory data including repeated values and results from unscheduled visits will be provided in data listings with indication of higher or lower than the associated normal range of each laboratory test.

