5.1.5 Laboratory Measurements

With the exception of urine pregnancy test, clinical laboratory tests will be performed by a central laboratory as specified in the regulatory binder.

Details for collecting, handling, and shipping samples (including shipment addresses) will be detailed in a separate laboratory manual. The Schedule of Visits and Procedures ([Table 1](#)) shows the time points at which urine samples will be collected for urinalysis and blood samples will be collected for clinical laboratory tests and plasma concentration levels.

[Table 2](#) presents the clinical laboratory tests to be performed. Metabolic parameters (including insulin, glucose, triglycerides, and total-cholesterol) and prolactin will be measured.

All laboratory tests will be reviewed in a timely manner by qualified site personnel to ensure safety. Abnormal lab findings may be confirmed if necessary by one repeated testing at the discretion of the Investigator. Any repeat laboratory testing will be conducted under **fasting condition as indicated**. Any laboratory abnormality may qualify as an AE in the Investigator's judgment.

Approximately 5.5 mL of blood per subject will be drawn at specified visits as per the schedule in [Table 1](#).

Table 2: Clinical Laboratory Tests

Category	Parameters
Hematology	RBC, WBC, Hgb, HbA1c ^a , HCT, MCH, MCHC, MCV, platelet count, and WBC with differential (neutrophils, lymphocytes, monocytes, eosinophils, basophils)
Chemistry	Electrolytes: Na ⁺ , K ⁺ , chloride, bicarbonate
	Liver function tests: alkaline phosphatase, AST, ALT, total bilirubin, direct bilirubin, indirect bilirubin
	Renal function parameters: BUN, creatinine
	Other: glucose, Ca ⁺² , albumin, phosphorus, lactate dehydrogenase, total protein, CK/CPK, globulin, uric acid, triglycerides, insulin, prolactin, cholesterol – total, HDL and LDL Amylase, gammaGT (GGT), Iron, Lipase, Magnesium
Urinalysis	Glucose, protein (total), ketones, bilirubin, urobilinogen, hemoglobin, leucocyte esterase, nitrite
Urine Drug Screen	Cocaine, amphetamines, barbiturates, benzodiazepines, cannabinoids, opioids, phencyclidine, propoxyphene, methadone and alcohol
Urine and Serum Pregnancy Test (FOCBP only)	hCG

a. This parameter will be measured **only** in subjects who participated in the 810P503 study.

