6.8.2 Laboratory Values

Clinical laboratory values will be summarized by visit using descriptive statistics for hematology and chemistry. For quantitative laboratory parameters, both actual values and change from Baseline values will be summarized.

Laboratory test results will be assigned a low, normal, high (LNH) classification according to whether the values were below (L), within (N), or above (H) the laboratory parameters' reference ranges provided by the central laboratory. By subject-listings of all abnormal laboratory values, i.e., those with L or H classification will be provided.

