# 3. GENERAL CONSIDERATIONS FOR DATA ANALYSES AND HANDLING

#### 3.1. General Statistical Methods

All statistical analysis will be performed using SAS version 9.4 or higher.

All data summaries will be presented by the optimized dose group (<18 mg/day; 18-<24 mg/day, 24-<36 mg/day or 36-54 mg/day) and overall. The optimized dose is defined as the first maintenance dose (at visit 5) for subjects entering maintenance period; otherwise using the end of study (EOS) dose for subjects discontinued prior to maintenance period.

Continuous variables will be summarized descriptively using number of subjects (n), mean, standard deviation (SD), median, minimum, and maximum.

Categorical variables will be summarized descriptively using counts and percentages. However, the number of patients with missing data will be excluded from the denominator for the percentage calculation. When the denominator for the percentage is different from the number of subjects in the treatment column header, the denominator will be clearly specified in the table or in a footnote for the table.

Individual subject data will be listed by subject ID. Unscheduled measurements (unless defined as baseline) will be excluded from summary tables but will be included in data listings. For assessments that are repeated or unscheduled, unless otherwise specified, the non-missing values from the first assessment will be used for generating summary statistics.

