#### 5.4.2. Clinically Notable ECG

The clinically notable QT interval corrected for Fridericia's method (QTcF) are presented in appendix **9.2**. The number and percentage of subjects with potentially post-baseline Clinically Notable Value(CNV) will be summarized by optimized dose group and overall. The denominator includes all subjects with non-CNV baseline and at least one post-baseline assessment (including unscheduled visit) and the numerator is the number of subjects with non-CNV baseline and CNV at post-baseline.

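### SAP 5.2.1 summarises laboratory tests only as by-visit descriptive statistics, so no laboratory table counts the subjects who become abnormal on prolactin, metabolic, liver or CK tests

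*SAP*

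**What the plan says.** SAP section 1 (Table 1) places clinical laboratory tests, with insulin, prolactin and urinalysis named, under the primary safety objective.

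SAP 5.2.1 then plans one type of laboratory table: absolute values and changes from baseline in "hematology, chemistry, and urinalysis continuous variables will be summarized descriptively at each scheduled visit". For two markers it adds a split: "Insulin and Prolactin will be summarized at each scheduled visit by sex and by the optimized dose group and overall". The statistics come from SAP 3.1: number of subjects, "mean, standard deviation (SD), median, minimum, and maximum". Repeats within a visit window are resolved by taking the first non-missing value. On other draws: "Results from unscheduled visits will not be included in this summary". SAP 3.4 sets the same exclusion for all descriptive statistics. Results above or below the normal range are marked in the data listings.

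Protocol 6.8.2 states: "Laboratory test results will be assigned a low, normal, high (LNH) classification". The only output it names for that class is by-subject listings of the L and H results.

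For QTcF, SAP 5.4.2 goes further. It counts subjects whose baseline is not notable and who have a notable value afterwards, and its denominator requires "at least one post-baseline assessment (including unscheduled visit".

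**The concern.** The safety question for a laboratory marker in a long extension study is how many subjects move from an acceptable value to an abnormal one. The protocol itself makes this central. Section 1.2 discusses the metabolic and prolactin effects of other antipsychotics and presents molindone as potentially neutral on weight and metabolism. Treatment may last 60 months.

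A by-visit mean and median describe the typical child at that visit. They move little when a minority changes a lot, and the visits are not linked within subject. Minimum and maximum show that someone was extreme, but not how many were. If the plan is followed exactly, the report could give mean prolactin by visit, sex and dose group, yet it could not state the proportion of children whose prolactin became high. A reader would have to count by hand from listings on about 600 subjects.

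**Working it through.** The documents give no event rate, threshold or precision target for laboratory tests, so there is no figure of theirs to reproduce. The check sets the text side by side and then uses labelled assumptions to show what the planned tables can and cannot yield.

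**1. Is there a count anywhere?**

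| Source | Subject-level count? | Unscheduled results |
|---|---|---|
| SAP 5.2.1, continuous laboratory variables | No | Excluded |
| SAP 5.2.1 and protocol 6.8.2, L/N/H status | No, listings only | Listed |
| SAP 5.1, TEAE tables | Yes, if the abnormality is recorded as an AE | Can contribute |
| SAP 5.4.2, QTcF | Yes | Included |

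SAP 3.1 gives counts and percentages to categorical variables in general. SAP 5.2.1 confines the laboratory summary to continuous variables and names no L/N/H table, so the general rule does not create one.

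**2. Scheduled draws.** Protocol Table 1 places hematology, chemistry and urinalysis at Visit 4 (Week 8), at the ten even-numbered visits from 6 to 24, and at Visit 25: 1 + 10 + 1 = 12 post-baseline draws.

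**3. Can by-visit results be converted into a share ever abnormal?** Suppose a proportion q were abnormal at each visit (assumed; the planned tables do not report even this). If the same children are abnormal every time, the ever-abnormal share is q. If visits are independent it is 1 − (1 − q)^m after m draws:

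| q per visit | Same children | m = 2 | m = 4 | m = 12 |
|---|---|---|---|---|
| 1% | 1% | 2.0% | 3.9% | 11.4% |
| 2% | 2% | 4.0% | 7.8% | 21.5% |
| 5% | 5% | 9.8% | 18.5% | 46.0% |

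The same by-visit rates are compatible with very different answers.

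**4. What does the mean show?** If a share p rises by k SD and the rest do not change, the mean moves by p × k SD. With k = 3 (assumed): 0.02 × 3 = 0.06 SD, 0.05 × 3 = 0.15 SD, 0.10 × 3 = 0.30 SD.

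The other statistics do help. Assume 5% rise by 40 ng/mL and the rest not at all. The mean change is 0.05 × 40 = 2 ng/mL, the median change 0, the maximum +40, and the SD of change 40 × √(0.05 × 0.95) = 8.7. The table would therefore show that a large rise occurred. It would not show that it occurred in 30 children (0.05 × 600), because in real data the SD also contains ordinary within-subject variation.

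**5. What would the missing table deliver?** Clopper-Pearson 95% intervals for assumed shares:

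- N = 600: 12 subjects (2%), 1.0 to 3.5%; 30 (5%), 3.4 to 7.1%; 60 (10%), 7.7 to 12.7%.
- An assumed dose group of 150: 8 subjects (5% is 7.5, rounded up), 2.3 to 10.2%.
- No events: upper limit 0.6% at 600 and 2.4% at 150.

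The figure of 600 is planned enrolment. The real denominator, limited to an eligible baseline and at least one later value, will be smaller and the intervals wider.

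**The case against.** The best defence has five parts.

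- **The tables are not means alone.** Correct. A reader might infer that an extreme value at a scheduled visit would go unseen, but the minimum, maximum and SD would show it. The number of subjects is still missing.
- **Abnormalities are counted as adverse events.** Partly correct. Protocol 5.1.1 counts abnormal laboratory findings among possible AEs, and also a deterioration that leads to symptoms, a treatment change or discontinuation. The TEAE tables in SAP 5.1 would count these, including any found between visits. However, protocol 5.1.5 leaves it to the investigator whether a laboratory abnormality is an AE, so the TEAE tables do not estimate the share of subjects with an abnormal value.
- **The SAP does what the protocol asked.** Correct. A reader might infer that the SAP dropped an L/N/H table, but protocol 6.8.2 promised only listings. The SAP even adds the split by sex and the urinalysis summary. The gap lies in both documents.
- **Nothing shows that unscheduled draws matter.** It is tempting to say that marked abnormalities are mostly first found there. The documents do not say so, and a sustained rise would also appear at the next scheduled visit. When an abnormal result is repeated within the window, the first-value rule keeps the original. The point does not depend on such a claim.
- **An any-time High count inflates by chance.** Correct, and important without a comparator. If 2.5% of draws in healthy subjects are flagged High, independently (assumed), 1 − 0.975^12 = 26% are flagged at least once over 12 draws. Protocol 5.1.5 mentions fasting only for repeat tests, so some metabolic flags may be non-fasting. This calls for careful presentation and does not justify having no count.

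A reader might also infer that urinalysis gets no table. Protocol Table 2 lists "Glucose, protein (total), ketones, bilirubin, urobilinogen, hemoglobin, leucocyte esterase, nitrite" without saying how each is reported. The most that can be said is that any parameter recorded in categories falls outside the continuous-variable summary.

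**Conclusion.** The point holds as a gap in planned output. Laboratory tests belong to the primary objective, and the plan as written cannot report the number or percentage of subjects who became abnormal on any laboratory test, except for those recorded as AEs. The text alone establishes this.

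Its size cannot be derived from the documents, which give no laboratory event rates. On the assumptions shown, a 5% share is 30 of 600 children while the mean moves by 0.15 SD for a 3 SD rise, and a 2% rate at each visit leaves the ever-abnormal share anywhere between 2% and 21.5%.

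No data are lost, since every result is listed with its flag, and no hypothesis test is affected. It is an inexpensive improvement that should be made because it changes what the study can conclude about laboratory safety.

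**What to change.** Add to SAP 5.2.1:

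- A baseline-to-worst-post-baseline L/N/H shift table for each test, covering subjects with a baseline and at least one post-baseline value.
- From it, n (%) of subjects not High at baseline (or not Low, where relevant) who become High (or Low) at any on-treatment time, including unscheduled and repeat results. Use the denominator logic of SAP 5.4.2: an eligible baseline and at least one post-baseline value. State whether Visit 25, drawn after the taper, counts as on treatment.
- Presentation by optimized dose group and overall, with prolactin and insulin also by sex.
- Subjects already abnormal at baseline kept visible in the shift table. Safety baseline is Visit 1 of this study, which follows conversion to SPN-810 and, for some subjects, earlier active treatment. A count of new abnormalities alone would miss rises that had already occurred.
- The same format for any urinalysis result recorded in categories.
- Preferably, pre-specified notable-value limits alongside the reference range, as SAP Appendix 9.2 does for QTcF, to reduce chance flags.

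Cost: a few more programmed tables and no new data, since protocol 6.8.2 already requires the classes. A footnote should state that any-time rates rise with the number of draws, with symptom-driven testing and possibly with non-fasting samples.

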# 5.3. Vital Signs and Body Size (Height/Weight/BMI)

#### 5.3.1. Absolute Value and Change from Baseline

CFB in vital sign and body size (Height/Weight/BMI) variables will be calculated for each scheduled post-dose visit. The analyses will be the same as described in Section **5.2.1**.

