Maximum duration of the study: Up to 60 months or until market availability.

- Optimization Phase: 8 weeks
- Maintenance Phase: initial period of 6 months, with the option for additional periods of 6 months each
- Taper Phase: 2 weeks

Safety Variables:

1. Adverse Events (AE) and Serious Adverse Events (SAE)
2. Extrapyramidal Symptoms (EPS) scales (Simpson-Angus Scale, Barnes Akathisia Scale, and Abnormal Involuntary Movement Scale)
3. Clinical Laboratory Tests (Hematology, Chemistry (Glucose, LDL, HDL, Triglycerides, Total cholesterol, etc.), Insulin, Prolactin and Urinalysis)
4. Concomitant Medications
5. Vital signs, Standardized BMI, Physical Examination and ECG (12-lead)
6. Columbia Suicide Severity Rating Scale (C-SSRS)

Efficacy Variables:

1. Retrospective-Modified Overt Aggression Scale (R-MOAS)
2. Clinical Global Impression – Improvement Scale (CGI-I)
3. Clinical Global Impression – Severity Scale (CGI-S)

Quality of Life Variables:

1. Child Health Questionnaire (CHQ-PF28)
2. Parenting Stress Index (PSI-4-SF) or Stress Index for Parents of Adolescents (SIPA)
3. Socio-demographics

Pharmacogenomics (PGx):

Participation in PGx testing is optional. For subjects already enrolled in this study, a blood sample for PGx analysis will be collected at the next visit following this amendment. For newly enrolled subjects, the blood sample for PGx analysis will be obtained at screening. Prior to testing, all subjects will be consented for PGx testing.

The DNA will be extracted and tested for any genetic variations associated with [REDACTED] enzyme. [REDACTED]

[REDACTED] The residual DNA will be stored for possible testing of genes involved in the efficacy and possible association with particular adverse events of the drug (e.g., understand the non-responders to treatment and/or individuals who show unusual safety profile). The DNA analysis will not be used for individual genetic characterization and the subject identity will be kept confidential. The PGx report may be a stand-alone document.

Analysis Populations:

All subjects who have documented Informed Consent/Accent and have taken at least one dose of SPN-810 during this study will be in the safety population.

Statistical Methods:

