3.2 Overall Study Design and Plan

Study 810P304 is a multicenter, open-label, extension study aimed to assess safety of SPN-810 in the treatment of IA in patients aged 6-17 years with ADHD in conjunction with standard ADHD treatment. The study has three phases: Optimization, Maintenance, and Taper.

All subjects who complete the randomized, double-blind portion of study 810P301, 810P302, 810P503 or 810P204 will have the option to participate in the OLE study in which all subjects will receive active Study Medication (SM) treatment. Subjects who choose to participate in the OLE will receive blinded conversion medication kits at Visit 6 of the previous SPN-810 double-blind randomization study (810P301, 810P302) or at Visit 4 for subjects completing the 810P204 study. Subjects, who have completed the 810P503 study and, chose to participate in this study, will receive the blinded conversion card at Visit 7.

Visit 7 of 810P301, 810P302 or Visit 8 for 810P503 will be Visit 1 of 810P304. Visit 6 of the 810P204 will be Visit 1 of the 810P304. The initial total daily dose for the OLE is [REDACTED]
[REDACTED]

After enrollment, eligible subjects will enter an optimization phase of two to eight weeks. Subjects will return to the office for visits at weeks 2, 4 and 8 during which the SM dose may be gradually adjusted based upon tolerability or effectiveness within the limits of [REDACTED]. The Investigator may gradually increase the dose of SPN-810 up to 54 mg/day for subjects with body weight \geq 30 kg. Following optimization, subjects will return to the office at each visit (every 3 months) during maintenance phase or until the subject discontinues or the study ends. The subject may discontinue at any time if the subject or the LAR withdraws IAF or ICF or if it is no longer in the best interest of the subject, at the investigator's discretion. If the subject discontinues or is removed from the study, he/she will taper off the SM over a period of at least 2 weeks.

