4.1.2 Exclusion Criteria

1. Body Mass Index (BMI) in the 99th percentile or above.

2. Clinically significant change in health status, safety concern or any other reason that, in the opinion of the Sponsor or the Investigator, would prevent the subject from participating in this study or successfully completing this study.
3. Pregnancy, breastfeeding or refusal to practice contraception during the study (for female subjects of childbearing potential and sexually active males).
4. Current substance or alcohol use.
5. Suicidal thoughts or behaviors confirmed at last visit in the previous double-blind randomized study.
6. Known allergy or sensitivity to molindone hydrochloride.

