6.8.3 Vital Signs, Height, Weight and BMI

Vital signs will be summarized by the group of the optimized doses (<18 mg/day; 18-24 mg/day, 24-36 mg/day or 36-54 mg/day) the subject received using descriptive statistics. Both actual values and changes from the Baseline to final visit will be summarized. Descriptive summary statistics (mean, SD, median, and range) for vital sign data, height, weight and BMI will be evaluated.

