#### **1. OBJECTIVES AND ENDPOINTS**

The objectives and endpoints are listed in Table 1.

rusie it objectives and Enapoints					
Objectives	Endpoints				
Safety Objective (Primary): Long-term safety on the use of SPN-810 as a treatment for impulsive aggression (IA) in subjects (6-17 years of age) with Attention Deficit/Hyperactivity Disorder (ADHD) when taken in conjunction with standard ADHD treatment only after satisfactory participation in a preceding double- blind study (810P301, 810P302,	
 
Endpoints         
 
Adverse Events
 
Extrapyramidal Symptoms (EPS) scales (Simpson-Angus Scale, Barnes Akathisia Scale, and Abnormal Involuntary Movement Scale)
 
Clinical Laboratory Tests (Hematology, Chemistry, Insulin, Prolactin and Urinalysis)
 
Concomitant Medications
 
Vital signs, Standardized BMI, Physical Examination and ECG (12- lead)
 
Columbia Suicide Severity Rating Scale (C-SSRS)
 
 
 
				
810P503 or 810P204). Efficacy Objective (Secondary): Long-term efficacy on the use of SPN-810 as a treatment for impulsive aggression (IA) in subjects (6-17 years of age) with ADHD when taken in conjunction with standard ADHD treatment.	
 
Change from Baseline (CFB) in Retrospective-Modified Overt Aggression Scale (R-MOAS) at each scheduled visit
 
Clinical Global Impression – Improvement Scale (CGI-I) at each scheduled visit
 
CFB in Clinical Global Impression – Severity Scale (CGI-S) at each scheduled visit
 
				
Quality of Life Objective (Exploratory): Long-term quality of life on the use of SPN-810 as a treatment for impulsive aggression (IA) in subjects (6-17 years of age) with ADHD when taken in conjunction with standard ADHD treatment.	
 
CFB in Child Health Questionnaire Parent Form 28-item (CHQ- PF28) at each scheduled visit
 
CFB in Parenting Stress Index – Short Form (PSI-4-SF) or Stress Index for Parents of Adolescents (SIPA) at each scheduled visit
 
Socio-demographics Characteristics
 
				

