# **3.2. Definitions and Derivations**

The general definitions and derivations are listed in Table 2.

Terminology	Definition			
Safety Baseline	Safety baseline is the last visit in double blinded studies (810P301, 810P302, 810P503 and 810P204), which is visit 1 in 810P304.			
Efficacy Baseline (R- MOAS and CGI-S assessments)	Efficacy baseline is defined as the last non-missing value collected prior to the first dose of the SM in the double-blind studies (810P301, 810P302, 810P503 and 810P204).			
Study Day	Day 1 is defined as the date of safety baseline. For visits prior to safety baseline, Study Day is calculated as (Visit Date – safety baseline). For visits after study safety baseline, Study Day is calculated as (Visit Date – safety baseline +1).			

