# 8. CHANGE FROM THE PROTOCL

Drug compliance in section 4.6 calculation was changed to use dose in mg instead of tablet because different tablet (ie. tablet) could be distributed in the same visit and

patient can take them interchangeably.

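### Standardized BMI is listed under the primary safety objective but is never defined or analysed; the planned height, weight and BMI tables mix expected growth with any excess gain

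*SAP*

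**What the plan says.** In SAP section 1, Table 1, the fifth endpoint under the primary safety objective reads "Vital signs, Standardized BMI, Physical Examination and ECG". The protocol synopsis carries the same item in its list of safety variables. These are the only two places where the term is used.

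The analysis sections name different variables. Protocol 6.8.3 states: "Descriptive summary statistics (mean, SD, median, and range) for vital sign data, height, weight and BMI will be evaluated". SAP 5.3.1 states: "CFB in vital sign and body size (Height/Weight/BMI) variables will be calculated for each scheduled post-dose visit", and refers to SAP 5.2.1 for the method, which is absolute value and change from baseline by visit, by optimized dose group and overall. Protocol 5.1.6 and the schedule of events likewise speak only of height, weight and BMI.

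SAP 3.2 says "The general definitions and derivations are listed in Table 2". That table covers safety baseline, efficacy baseline and study day, and nothing on BMI. SAP section 8 has one entry: "Drug compliance in section 4.6 calculation was changed to use dose in mg instead of tablet".

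A BMI norm appears elsewhere only at entry, where Protocol 4.1.2 excludes "Body Mass Index (BMI) in the 99th percentile or above". No growth reference is named.

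**The concern.** There are two problems.

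The first is a mismatch between the endpoint list and the analysis. A programmer who follows the SAP will produce no output for Standardized BMI, and nothing in the SAP says it was dropped.

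The second is interpretation. In children and adolescents, height, weight and BMI change with age. Protocol 3.2 describes a study "in which all subjects will receive active Study Medication (SM) treatment", so no concurrent untreated group shows what growth alone would have done. Over as long as 60 months, an unadjusted mean change is expected growth plus whatever else happened, and the table cannot separate them.

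This matters here because Protocol 1.2 gives molindone's apparent neutrality for weight and metabolism as a reason for interest in the drug. Readers will look to these tables for long-term evidence on that point. If a reference and an age rule are chosen only after the data are seen, the result will carry less weight than a pre-specified one.

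**Working it through.** The plan gives no figure for this variable, so the check is mainly textual, followed by short arithmetic on scale.

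**1. Does each safety endpoint in SAP Table 1 have an analysis or listing?**
- Adverse events: SAP 5.1
- EPS scales: SAP 5.6
- Laboratory tests: SAP 5.2
- Concomitant medication: SAP 4.5
- Vital signs: SAP 5.3
- Physical examination: SAP 5.5
- ECG: SAP 5.4
- C-SSRS: SAP 5.7
- Standardized BMI: none

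The cross-reference from 5.3.1 to 5.2.1 does not fill the gap. In 5.2.1 only insulin and prolactin are split by sex, and nothing is adjusted for age. The only z-scores in the SAP belong to CHQ-PF28 (SAP 7.1).

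**2. How many summaries are affected?** The schedule of events takes weight, height and BMI at Visits 1 to 25. Visit 1 is baseline, so 25 − 1 = 24 post-baseline visits are summarized without adjustment.

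**3. How much ambiguity do unadjusted means leave?** Protocol 1.3 reports 810P203, the earlier 6-month open-label extension. Group-mean gains were 2.18-3.70 kg and 0.55-1.06 kg/m². Most of the increase is attributed to normal growth, and no standardized value is given. Take most to mean a growth share *g* of 50-100%, and apply it equally to weight and BMI and to each group (assumptions). Then excess = (1 − *g*) × mean gain:
- Largest BMI gain: (1 − 1.0) × 1.06 = 0 to (1 − 0.5) × 1.06 = 0.53 kg/m²
- Largest weight gain: 0 to 0.5 × 3.70 = 1.85 kg
- Smallest gains: 0 to 0.5 × 0.55 = 0.275 kg/m², and 0 to 0.5 × 2.18 = 1.09 kg

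This illustrates what a reader is left with when only raw means are reported. It does not estimate a drug effect. Maximum follow-up here is 60/6 = 10 times as long; no 60-month value is projected, because linear extrapolation has no support.

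**4. Could dose groups serve as the comparison?** Not reliably. SAP 3.1 sets the groups by the Visit 5 dose, or by the end-of-study dose for those who leave before maintenance. Starting dose differs by parent study (Protocol 1.4: 18 mg/day from the studies in children, 36 mg/day from the adolescent study). Doses above 36 mg/day are tied to a body weight of at least 30 kg (Protocol 3.2.4). Groups may therefore differ in age and size.

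**5. How far would a growth reference reach?** Subjects entering at 6 to 17 are 6 + 5 = 11 to 17 + 5 = 22 at month 60, counted from the birthday. If the reference ends at age *L* = 18 to 20 (assumption), anyone entering after *L* − 5 = 13 to 15 passes it by month 60. A subject entering on the 17th birthday passes it at (18 − 17) × 12 = 12 to (20 − 17) × 12 = 36 months. One entering just under 18 passes an 18-year limit almost at once and a 20-year limit at about month 24.

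**The case against.** The strongest reply is that the term is a loose label for plain BMI. Every body section of both documents says height, weight and BMI, and the extra word appears only in a bundled list carried from the synopsis into SAP Table 1. On that reading the endpoint is analysed and one word is wrong. This cannot be ruled out. Even so, Table 1 would need correcting, and the unadjusted tables would still not separate growth from excess gain.

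It can also be said that the label primary gives the point too much weight: Protocol 1.5 names treatment-emergent adverse events, concomitant medications and EPS frequency as the primary outcome measures. That is a fair limit on its importance. The placement under the primary safety objective is nevertheless the SAP's own.

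Third, the information is largely kept. Height is tabulated beside BMI, individual data are listed, and BMI-for-age could be derived later if age at each visit is available. What is lost is a pre-specified definition and table. Weight-gain adverse events help too, as they did in 810P203, but they depend on investigator judgment and are not a uniform measurement in every subject.

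Finally, the 810P203 range rests on an assumed share, and no table from this study could narrow it for that earlier one. That stands; the range shows ambiguity only, and the conclusion does not depend on it.

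**Conclusion.** The concern holds. Standardized BMI is listed in both documents and defined, derived and summarized in neither, with no recorded removal. Unless plain BMI was meant, the plan produces no table for an endpoint listed under the primary safety objective. On either reading, body-size change at all 24 post-baseline visits is reported without allowance for growth, in subjects aged 6-17, for up to 60 months, with no control arm.

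Reading the term as age- and sex-standardized BMI is an inference. It is the natural one for this age range, and the percentile exclusion at entry shows that a growth norm is already implied. The study is descriptive, with no power or sample-size basis (Protocol 6.12), so the effect is on interpretation of the safety tables and on no formal test. The change should be made.

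**What to change.** In SAP Table 2, define Standardized BMI as an age- and sex-specific BMI z-score, with percentile, from a named growth reference and using age at each visit. State a rule for subjects beyond the reference's age range: for example, report the z-score only up to the upper limit, show n at each visit, and give unstandardized BMI after that.

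In SAP 5.3.1, add value and change from baseline by visit, by optimized dose group and overall. Keep unstandardized height, weight and BMI as supportive. State two limits:
- The z-score shows departure from expected growth and does not by itself attribute it to drug, because there is no control arm and ADHD medication may change during the study (Protocol 4.3.1).
- Safety baseline is the last double-blind visit, so any change before entry is not captured.

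If plain BMI was meant, or the endpoint is not wanted, correct Table 1 and record it in section 8.

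The cost is SAP wording, one derivation and one set of table rows. Height and weight are taken at every visit, and age and sex are recorded (SAP 4.3). Two things need confirming: which reference was used for the entry percentile, and whether birth date or age in months is captured, which the documents do not say. Late-visit values will be missing or rule-based for older adolescents.
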